6.11. Important Protocol Deviations

Important protocol deviations are specified in the Trial Issues Management Plan (TIMP). A listing and a summary of important protocol deviations by treatment will be provided.

6.12. Efficacy Analyses

For the Food and Drug Administration (FDA) and potentially for other regulatory agencies, primary and key secondary efficacy assessments will be guided by the “treatment-regimen” estimand conducted using the FAS. Assessment of the primary and secondary efficacy objectives subject to type 1 error rate control (key secondary) will be conducted with multiple imputation of missing data (see Section 6.12.1.3) at 40 weeks. For publications and other purposes, the

assessment of efficacy objectives will be guided by the “efficacy” estimand using the EAS without imputation of missing data. A listing of patients randomized but not included in efficacy analyses (not treated or discontinued treatment due to inadvertent enrollment) will be provided.

6.12.1. Primary Efficacy Analysis

The primary efficacy measure will be change in HbA1c (% and mmol/mol) from baseline (postbaseline – baseline). Both HbA1c values as well as change from baseline in HbA1c will be summarized by treatment and nominal visit (week). When applicable, HbA1c data from the local lab will be used when central lab data is not available. If scheduled HbA1c data at the primary endpoint visit is not available, unscheduled HbA1c data collected for the primary endpoint visit will be included in the analysis.

6.12.1.1. Primary Analysis Relative to the Efficacy Estimand

The primary analysis relative to the “efficacy” estimand will be conducted using HbA1c data in the EAS from baseline through the 40-week visit with the aid of a mixed-model repeated measure (MMRM). Restricted maximum likelihood (REML) will be used to obtain model parameter estimates and the Kenward-Roger option will be used to estimate denominator degrees of freedom. The response variable of the MMRM model will be the primary measure and model terms of interest will include treatment, visit, treatment-by-visit interaction, country/pooled country, and baseline metformin use (Yes/No) as fixed effects, and baseline HbA1c as a covariate. An unstructured covariance matrix will be used to model the within-patient errors. If this model fails to converge, the following covariance structures will be tested in the following order:

1. Heterogeneous Toeplitz
2. Heterogeneous First Order Autoregressive
3. Heterogeneous Compound Symmetry
4. Toeplitz
5. First Order Autoregressive, and
6. Compound Symmetry.

The first covariance structure that converges will be used. The resulting least squares mean (LSM) estimate of mean change from baseline in HbA1c will be summarized by visit and by study treatment.

With the aid of the MMRM analysis, p-values, and 2-sided 95% confidence intervals (CIs) for mean change in HbA1c from baseline to the 40-week visit will be derived and summarized for the 5 mg, 10 mg, and 15 mg doses of tirzepatide compared to placebo.

6.12.1.2. Primary Analysis Relative to the Treatment-Regimen Estimand

The primary analysis relative to the treatment-regimen estimand will be conducted utilizing HbA1c data in the FAS at baseline and at the 40-week visit with the aid of an ANCOVA model.

The response variable will be the primary measure and model terms will include treatment, country/pooled country, and baseline metformin use (Yes/No) as fixed effects and baseline HbA1c as a covariate. The ANCOVA analysis will be conducted using multiple imputation of missing primary measures (see Section 6.12.1.3 for details) and statistical inference over multiple imputation of missing data guided by Rubin (1987).

With the aid of the ANCOVA analysis, p-values and 2-sided 95% CIs for mean change in HbA1c from baseline to the 40-week visit will be derived and summarized for the 5 mg, 10 mg, and 15 mg doses of tirzepatide compared to placebo.

6.12.1.3. Methods for Multiple Imputations

For efficacy analyses relative to the “treatment-regimen” estimand, missing HbA1c data at the 40-week visit will be imputed based on “retrieved dropouts,” defined as patients who had their HbA1c value measured at the 40-week visit in the same treatment arm who prematurely discontinued study drug. A pseudo-SAS program for implementing multiple imputations using data from retrieved dropouts is included in [Appendix 1](#). In cases where there are not enough retrieved dropouts to provide a reliable imputation model, an alternative multiple imputation method with reference to the placebo group (placebo multiple imputation) will be used as the primary analysis relative to the treatment-regimen estimand. Analyses will be conducted with multiple imputations, and statistical inference over multiple imputations will be guided by the method proposed by Rubin (1987). If the primary analysis using “retrieved dropouts” for imputation converges, the analysis using “placebo multiple imputation” to impute the missing data will be conducted as a sensitivity analysis. If value of the imputed HbA1c change from baseline is $<-6.0\%$ or $>6.0\%$, that value will be set to -6.0% or 6.0% , respectively, to avoid unrealistic imputed values.

6.12.2. Secondary Efficacy Analyses Subject to Type 1 Error Rate Control

6.12.2.1. Analyses of Continuous Outcomes

Analyses for change from baseline in body weight as well as fasting serum glucose (FSG; postbaseline – baseline) will be conducted in a manner similar to the primary analyses in Section 6.12.1. Baseline HbA1c category ($\leq 8.0\%$, $>8.0\%$ [≤ 64 , >64 mmol/mol]) will be used as a fixed factor in place of baseline HbA1c as a covariate and baseline of the corresponding variable will be used as an additional covariate in the statistical model. Least squares mean estimates of mean change in body weight and FSG from baseline will be summarized by nominal visit and by study treatment. When applicable, fasting glucose data from a local lab will be used when central lab data is not available. For the multiple imputation of missing values, if value of the imputed weight change from baseline is <-50 kg or >50 kg, that value will be set to -50 kg or 50 kg, respectively, to avoid unrealistic imputed values; if value of the imputed fasting serum glucose change from baseline is <-20 mmol/L or >20 mmol/L, that value will be set to -20 mmol/L or 20 mmol/L, respectively, to avoid unrealistic imputed values.

6.12.2.2. Analyses of Binary Outcomes

The analysis relative to the “efficacy” estimand for the endpoint at 40 weeks will be performed using EAS with missing values imputed from an MMRM model and then dichotomized. The MMRM model includes treatment, country/pooled country, baseline metformin use (Yes/No), visit, and treatment-by-visit interaction as fixed effects, and baseline HbA1c as a covariate. After dichotomizing continuous HbA1c, the data is analyzed using a logistic regression model with treatment, country/pooled country, baseline metformin use (Yes/No) as fixed effects, and baseline HbA1c as a covariate. In addition, analysis will be conducted utilizing data using EAS from baseline through the 40-week visit with the aid of a longitudinal logistic regression with repeated measurements with treatment, visit, treatment-by-visit interaction, country/pooled country, and baseline metformin use (Yes/No) as fixed effects and baseline HbA1c as a covariate. In case the longitudinal logistic model does not converge due to small number of events, logistic regression will be utilized to analyze proportion of patients achieving HbA1c targets at nominal visits.

The analysis relative to the “treatment-regimen” estimand will be conducted utilizing HbA1c data in the FAS at baseline and at the 40-week visit with the aid of a logistic regression using multiple imputation of missing HbA1c data at the 40-week visit (see Section 6.12.1.3 for details). Model terms will include treatment, country/pooled country, and baseline metformin use (Yes/No) as fixed effects, and baseline HbA1c as a covariate. Statistical inference over multiple imputations will be guided by Rubin (1987).

6.12.3. Type 1 Error Rate Control Strategy for Primary and Key Secondary Efficacy Analyses

Since they are intended for different purposes, no type 1 error rate adjustments will be made for conducting analyses relative to “efficacy” and “treatment-regimen” estimands. For analyses within each estimand, the type 1 error control strategy for evaluation of the primary and key secondary objectives is illustrated in [Figure GPGI.6.1](#).

The type I error rate control strategy for the Pharmaceuticals and Medical Devices Agency (PMDA) is in [Appendix 2](#).

1. $H_{15,1}$ and $H_{15,2}$ are evaluated hierarchically each at a 2-sided 0.025 significance level conditioned on successfully achieving the preceding objective. In parallel,
2. $H_{10,1}$ and $H_{10,2}$ are evaluated hierarchically each at a 2-sided 0.025 significance level conditioned on successfully achieving the preceding objective.
3.
 - a. If all objectives in #1 and #2 above are successfully established, $H_{5,1}$ and $H_{5,2}$ are evaluated hierarchically, each at a 2-sided 0.05 significance level.
 - b. If all objectives in only #1 or only #2 above are successfully established, $H_{5,1}$ and $H_{5,2}$ are evaluated hierarchically, each at a 2-sided 0.025 significance level.
4. If both objectives: $H_{5,1}$ and $H_{5,2}$ are successfully established and
 - a. If all objectives in #1 and #2 above are successfully established, then $H_{10,3}$, $H_{15,3}$, $H_{10,4}$, $H_{15,4}$, $H_{5,3}$, $H_{5,4}$, $H_{15,5}$, and $H_{10,5}$ will be evaluated hierarchically each at a 2-sided 0.05 significance level conditioned on successfully achieving the preceding objective.
 - b. If all objectives in only #1 or only #2 above are successfully established, then $H_{10,3}$, $H_{15,3}$, $H_{10,4}$, $H_{15,4}$, $H_{5,3}$, $H_{5,4}$, $H_{15,5}$, and $H_{10,5}$ will be evaluated hierarchically each at a 2-sided 0.025 significance level conditioned on successfully achieving the preceding objective.
5. If all objectives in #3, #4, and #5 above are successfully established, and at least 1 objective from #1 or #2 above is not successfully established, recycle 100% of the unused alpha back to #1 or #2 above.

[figure not shown]

Figure GPGI.6.1. Type 1 error control strategy for primary and key secondary efficacy endpoints.

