6.1. Populations for Analyses

For purposes of analysis, [Table GPGI.6.1](#) defines analysis populations/data sets.

Table GPGI.6.1. Analysis Populations/Data Sets

Population/Data Set	Description
Screened population	All participants who sign informed consent
Randomized population	All patients who are randomly assigned a treatment arm
Modified intention-to-treat (mITT) population	All randomly assigned participants who are exposed to at least 1 dose of study drug. In the event of a treatment error, participants will be analyzed according to the treatment they were randomized.
Efficacy analysis set (EAS)	Data obtained during Study Period II from the mITT population, excluding patients discontinuing study drug due to inadvertent enrollment and data after initiating rescue antihyperglycemic medication or early discontinuation of study drug (last dose date + 7 days).
Full analysis set (FAS)	All available data obtained during Study Period II from the mITT population, regardless of adherence to study drug or initiation of rescue antihyperglycemic medication. Patients who discontinued study drug due to inadvertent enrollment will be excluded.
Safety analysis set (SS)	All available data obtained during Study Periods II and III from the mITT population, regardless of adherence to study drug or initiation of new antihyperglycemic medication.

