6.2. General Considerations

Statistical analysis of this study will be the responsibility of Eli Lilly and Company (Lilly) or its designee. All statistical analyses will be conducted with SAS Version 9.4 or higher unless otherwise stated. Any change to the data analysis methods described in the protocol will require an amendment only if it changes a principal feature of the protocol. Any other changes to the data analysis methods described in the protocol, and the justification for making the change, will be described in the SAP or the clinical study report (CSR). Some analyses and summaries described in this analysis plan may not be conducted if not warranted by data (e.g., few events to justify conducting an analysis). Listings of events will be provided in such situations. Additional analyses of the data may be conducted as deemed appropriate without further changes made to the protocol or SAP, even after the primary or final database locks (DBL).

Additionally, to avoid potential selection biases, unless stated otherwise, statistical summaries and analyses will be conducted based on randomized maintenance dose regardless of the actual treatment received by the patient.

Unless specified otherwise, the last measurement during Visit 1 to Visit 3 (including unscheduled visits) collected prior to or on the first dose day will serve as baseline.

- For immunogenicity, data collected up to the first dose time will serve as baseline.
- For lab and ECG, baseline needs to be prior to or within one hour after the first dose time.
- For patient-reported outcomes, data collected at Visit 3, regardless of the timing relative to first dose, will serve as baseline.

There will be 2 estimands of interest in evaluating the primary and secondary efficacy objectives. The first estimand, the “efficacy” estimand, represents efficacy prior to discontinuation of study drug without the confounding effects of rescue therapy for severe persistent hyperglycemia. Analyses relative to the “efficacy” estimand will be conducted using the efficacy analysis set (EAS). The second estimand, the “treatment-regimen” estimand, represents the efficacy irrespective of adherence to investigational product or introduction of rescue therapy for severe persistent hyperglycemia. Analyses relative to the “treatment-regimen” estimand will be conducted using the full analysis set (FAS).

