6.4. Handling of Dropouts or Missing Data

For the primary and secondary efficacy endpoint analyses subject to type 1 error rate control, data for patients with missing values at the 40-week visit will be imputed based on the method described in Section 6.12.1.3. Unless specified otherwise, imputation of missing data will be limited to primary and key secondary efficacy endpoint analyses. Any other secondary or exploratory efficacy parameter values or safety laboratory values that are missing will not be explicitly imputed.

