Appendix 1. SAS Code for Multiple Imputation

```
*retrieved dropout imputation*;
*ret fl is a flag variable for subjects that are retrieved dropouts*;
proc mi data=&dataset_in. seed=&seed. out=&dataset_out. nimpute=&n_impute.;
by trtpn;
class ret_fl;
monotone reg(chg/details);
mnar model (chg/modelobs=(ret_fl='Y'));
var base chg;
run;

[figure not shown]
*placebo imputation*;
*replace 'placebo' with the assigned value for the placebo group*;
proc mi data=&dataset_in. seed=&seed. out=&dataset_out_2. nimpute=&n_impute.;
class trtpn;
monotone reg(chg/details);
mnar model (chg/modelobs=(trtpn='placebo'));
var base chg;
run;
```

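### SAP 6.12.2.2 gives no pooling step for the efficacy-estimand HbA1c targets; followed literally, it analyses a single MMRM fill as observed data, so standard errors are too small

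*SAP*

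**What the plan says.** The targets concerned are <7.0% for all three doses and <5.7% for 10 and 15 mg, which SAP 4.2 places under type 1 error control.

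- **SAP 6.12.2.2, efficacy estimand.** The analysis "will be performed using EAS with missing values imputed from an MMRM model and then dichotomized". The dichotomised data then go into a logistic regression on treatment, country, metformin use and baseline HbA1c. A longitudinal logistic regression on the EAS is added, without saying which of the two feeds the testing scheme.
- **SAP 6.12.2.2, treatment-regimen estimand.** This paragraph names multiple imputation, refers to 6.12.1.3 and ends: "Statistical inference over multiple imputations will be guided by Rubin (1987".
- **SAP 6.4.** For all type 1 error-controlled endpoints, "data for patients with missing values at the 40-week visit will be imputed based on the method described in Section 6.12.1.3". No estimand is named.
- **SAP 6.12.1.3.** It opens: "For efficacy analyses relative to the “treatment-regimen” estimand, missing HbA1c data at the 40-week visit will be imputed based on" retrieved dropouts, with placebo-based imputation as the alternative.
- **SAP 6.12.** After the FDA sentence, it says controlled objectives are assessed with multiple imputation. It then says that, for publications and other purposes, efficacy is guided by the efficacy "estimand using the EAS without imputation of missing data".
- **Protocol 10.3.3.2.** For <7.0% under the efficacy estimand, patients without a Week 40 value are left out.

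**The concern.** A filled value is a guess. If one guess per patient is treated as a measurement, the logistic model counts 118 patients per arm as observed when fewer were, and the uncertainty of the guess is lost. Confidence intervals become too narrow and the test can reject too often.

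If the fill is the MMRM predicted mean, there is a second problem. Predicted means are less spread out than real values, so they cross a cut-off less often from either side. Dichotomising them pushes each arm's responder proportion away from 50%. When one arm mean lies above 7% and the other below, the treatment difference is exaggerated.

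The endpoint carries alpha, so whether the imputation is single or multiple should be settled before database lock.

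**Working it through.** **The plan's own figure.** SAP 5.2 gives 0.6% difference, SD 1.1, two-sided 0.025, 90% power and up to 28% rescued or discontinued. Evaluable per arm: 2 × (2.2414 + 1.2816)² × (1.1/0.6)² = 83.4, so 84. Then 84/0.72 = 117 per arm, or 468. By the exact t-test it is 85 per arm (power 90.1%); 118 × 0.72 = 85 and 4 × 118 = 472. The stated sample size is reproduced and is not in question. At the 28% ceiling, 118 × 0.28 = 33 patients per arm would need a fill.

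**Can another section supply the pooling?**

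- SAP 6.4 leads to 6.12.1.3, but that section is limited to the other estimand and uses retrieved-dropout or placebo models, not an MMRM.
- Retrieved-dropout imputation cannot be run on the EAS, which excludes "data after initiating rescue antihyperglycemic medication or early discontinuation of study drug (last dose date + 7 days".
- Appendix 1 codes only those two methods, for example "mnar model (chg/modelobs=(ret_fl='Y"; it contains no MMRM.

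**Bias of a predicted-mean fill, in closed form.** Assumed: Week 40 SD 1.1, arm means 7.4 and 6.8, missing completely at random. Let r be the correlation between the MMRM prediction and the true value. True proportion below 7% is Φ((7 − mean)/1.1): 0.358 and 0.572, difference 0.214. Among filled patients it is Φ((7 − mean)/(1.1r)). The reported difference is the weighted mix.

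- r = 0.5: filled proportions 0.234 and 0.642, difference 0.408. With 28% missing: 0.72 × 0.214 + 0.28 × 0.408 = 0.268. With 10%: 0.9 × 0.214 + 0.1 × 0.408 = 0.233.
- r = 0.7: filled difference 0.301; 0.238 with 28% missing.
- r = 0.85: filled difference 0.250; 0.224 with 28% missing.

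Simulation agrees (0.240 to 0.268 for r = 0.5 to 0.7; 0.223 for r = 0.85). Coverage of the 95% interval at 28% missing was 77 to 89% for r = 0.5 to 0.7 and 93% for r = 0.85. With means 8.2 and 7.6, both above the cut-off, the mean fill reports 0.147 to 0.158 against a true 0.155, so the bias largely disappears. One random draw is unbiased but covers only 91 to 94% at 28% missing.

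**Standard errors.** Rubin's total variance is T = W + (1 + 1/m)B, with W the within-imputation variance, B the between-imputation variance and m the number of imputations. A single fill reports W alone. If k is reported standard error over true SD, size at nominal 0.05 is about 2Φ(−1.96k). For k = 0.725 this gives 0.155 (simulated 0.150); for k = 0.872 it gives 0.087 (simulated 0.087).

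**Stand-alone type 1 error for <7%, nominal 0.05, 118 per arm.** In the first simulation, Week 40 HbA1c depends on baseline and one earlier-visit predictor:

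| Setting | Mean fill | One draw |
|---|---|---|
| Null means 7.0–7.5, 28% missing, r 0.5–0.7 | 0.083–0.152 | 0.074–0.104 |
| Same means, 28%, r 0.85 | 0.063–0.067 | 0.064–0.066 |
| Same means, 10%, r 0.5–0.85 | 0.053–0.081 | 0.053–0.070 |
| Null means 8.2, 28% | 0.055–0.063 | 0.058–0.077 |

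Complete data gave 0.043 to 0.054. A second simulation used seven HbA1c visits and monotone dropout, with 15 to 50% at target. At 28% missing it gave k = 0.73 to 0.94 and size 0.059 to 0.150 (mean fill), and k = 0.87 to 0.93 and size 0.058 to 0.087 (one draw). At 10% missing size was 0.060 to 0.073, and at 5% it was 0.050 to 0.056.

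**Family-wise error.** The scheme's figure is not shown, so <7% is taken as hypothesis 3 from the order of objectives. In step 4a, a dose with no HbA1c effect has already been falsely declared superior on HbA1c change, so a false target claim adds no family-wise error. In step 4b, tests run at 0.025 and one of 10 or 15 mg may be inert while the other and 5 mg succeed. With 10 mg inert and other gates taken as passed, the error on that route against a ceiling of 0.05 is:

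- null means 7.0–7.5, 28% missing, r 0.5–0.7: 0.060 to 0.107 (mean fill), 0.056 to 0.074 (one draw);
- 10% missing: 0.047 to 0.057 and 0.043 to 0.052;
- r = 0.85, 28% missing: 0.050 to 0.051.

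Complete data gave 0.038 to 0.048. These family-wise figures and the coverage figures come from the first simulation only.

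**The case against.** The SAP never says single imputation, and the largest figures need a second unstated choice, a predicted-mean fill. Several passages point towards multiple imputation. SAP 6.12 names it for controlled objectives, and SAP 6.4 sends all of them to a section that contains Rubin's rules. A fair reader could take 6.12.2.2 as changing the imputation model and leaving the inference rule in place. The absence of a number of imputations proves nothing, since Appendix 1 leaves both that number and the seed as unvalued macro variables for methods that are plainly multiple. All of this stands, and it is why the literal reading is an inference. It does not close the gap: the sentence in 6.12 follows the FDA sentence, and 6.12.1.3 confines itself to the other estimand and other models.

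A reader might also infer that four analyses are equally open: single fill, multiple imputation, no imputation and exclusion. The documents do not support that. SAP 6.12.2.2 is the specific rule for this endpoint, and SAP 6.2 allows the SAP to replace a protocol method, provided that "the justification for making the change, will be described in the SAP or the clinical study report (CSR". The live question is single or multiple.

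The exposed step 4b route is narrow. Protocol 3.2 reports dose-dependent HbA1c lowering at all three doses in Phase 2, so an inert 10 or 15 mg dose beside an effective 5 mg dose is unlikely, although strong control formally covers it. HbA1c is measured six times from Week 4 to Week 24 and glycemic rescue criteria start at Week 16, so r may be high for rescued patients. The 28% is a ceiling. The longitudinal logistic regression, which uses no fill, gives a cross-check.

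**Conclusion.** The point holds as a gap with a definite direction. The efficacy-estimand paragraph of SAP 6.12.2.2 omits the step that would make its standard errors valid, and an analyst who follows it literally will report intervals that are too narrow.

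The size is conditional on r, the arm means, the amount missing and the fill method, none of which is fixed by the documents. At the 28% ceiling with r = 0.5 to 0.7 and null means near 7.0 to 7.5, stand-alone type 1 error is about 0.07 to 0.15; at 10% missing or r = 0.85 it is about 0.05 to 0.08. The simulations assume missingness completely at random and omit the country and metformin terms, so they are indicative.

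Two stronger readings should be resisted. The trial's family-wise error is not shown to be inflated in general; the exposure is mainly step 4b. For <5.7%, which on the assumed labelling is tested last, the issue is interval width. Nor are regulatory decisions at risk: FDA relies on the treatment-regimen estimand, and the PMDA scheme in Appendix 2 controls only HbA1c change and body weight. What is affected is the efficacy-estimand result used for publications and other purposes. This should be fixed, with medium confidence in the size.

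**What to change.** In SAP 6.12.2.2, state that missing Week 40 values under the efficacy estimand are multiply imputed by random draws from the stated MMRM on EAS data, with parameter and residual uncertainty. Dichotomise within each completed data set, fit the stated logistic model and combine by Rubin's rules. Say that this analysis carries the alpha and that the longitudinal logistic regression is supportive. Align SAP 6.4 and 6.12 with it, and record why the protocol's exclusion rule is replaced. The number of imputations and the seed can be set in the program, as in Appendix 1.

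The cost is wording and a short program, with no new data. Compared with a mean fill, intervals widen by 3–5% (10% missing) or 8–16% (28%) at means 7.4 and 6.8, and by 4–7% or 10–23% at 8.2 and 7.6. The pooled test is conservative, mildly at 10% missing (type 1 error 0.031 to 0.043) and more so at 28% (0.015 to 0.036), against 0.040 to 0.055 for exclusion. Power at 28% missing still exceeds that of exclusion: 0.88–0.91 against 0.82–0.84 (7.4 and 6.8), and 0.78–0.81 against about 0.73 (8.2 and 7.6).
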